9.3 POPULATIONS FOR ANALYSES

Intent-to-treat analyses will be used and all participant's data will be analyzed according to their random group assignment.

9.4 STATISTICAL ANALYSES

9.4.1 GENERAL APPROACH

All statistical tests, except for the exceptions noted here, will be conducted at an alpha level of 0.05.

Exceptions: The 16-week and 32-week tests of intervention effect on the primary and secondary outcomes will be conducted using a Bonferroni-corrected alpha level of 0.025.

For every primary endpoint, a linear mixed model will be built for the outcome at all three follow-up timepoints (16, 32, and 48 weeks) with the following fixed effects: intercept, value of the endpoint at baseline, timepoint (three parameters total, with baseline as the referent), intervention (control as the referent), and intervention by timepoint interaction (three parameters total, allows for a different intervention effect at each timepoint). The test of the outcome at 48 weeks will be a test of the coefficient for the intervention effect at 48 weeks.

A random intercept will be included to account for within-participant correlation. For the primary outcome, modeled at the three follow-up visits, the within-subject covariance matrix will be chosen based in the lowest AIC among unstructured, compound symmetric, and first-order autoregressive. To improve model fit, transformation of non-normal (i.e., highly skewed) endpoints will be considered. If imbalance is detected among the randomized groups on one or more variables associated with the outcome (identified in section 9.4.4), these variables will also be included in the model.

The fixed-effects can be interpreted like multiple regression parameters and provide basis for population regression lines. The random- effects component allows variation among participants. This plan accounts for within-subject correlations between measurements from the same individual across time.

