9.2 SAMPLE SIZE DETERMINATION

200 participants will be enrolled (100 each in HARMONY and NEEW). Conservatively, based on prior research, comparisons of complete data on 80 participants per group are assumed, and also assume 20% attrition. Power calculations were performed with POWERLIB20 SAS/IML modules that incorporate methods to calculate power for the general linear multivariate model, which includes repeated measures data structures. Based on pilot study data, power analysis focuses on a group of representative variables addressed in the primary and secondary endpoints for CM risk factors. For primary and secondary endpoints, power is based on a separate multivariate model for these outcomes, incorporating measures from all timepoints. It is hypothesized that through improvements in self-management, women in HARMONY (experimental group) will show greater sustained improvements in exercise and healthy eating behaviors (primary endpoint) and greater reduction of CM risk biomarkers (secondary endpoint). Each hypothesis will be considered by specifying both a between-group contrast (HARMONY vs. NEEW) and the appropriate within-group contrast (three post-baseline timepoints versus baseline). This facilitates testing the null hypothesis that both groups have the same difference in population means for the change from baseline at a specific post-baseline time point against the alternative that the between-group difference of the change from baseline significantly differs from 0.

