The primary endpoint at 48 weeks post first group session is tested at a significance level of 0.05; the other two timepoints will be tested using a Bonferroni correction of a two-sided 0.025 ($=0.05/2$) significance level. A compound symmetry correlation structure is assumed across all timepoints in our calculations. Based on pilot data, correlation parameters are 0.35 for BMI, 0.11 for WHR and -0.45 for A1C. With 80 participants per group (total of 160), statistical power is 85% to detect an effect size of 0.56 for BMI and exceeds 95% to detect an effect size of 0.45 for A1C and 0.59 for waist-hip ratio at each post-baseline time point.^{76,94} In tertiary endpoints, it is hypothesized that mediation of the intervention effect on the primary outcomes (exercise and healthy eating) by the tertiary outcomes (improvements in self-reported mindfulness, stress management, positive reappraisal, self-regulation, and self-efficacy). [In simulations of power for mediation tests, Fritz and Mackinnon⁹⁵ found that when effect sizes (standardized regression coefficients) relating the intervention to the mediator and the mediator to the outcome are all ≥ 0.26 (small- medium, according to Cohen's [1988] definition)⁹⁶, the sample size ($n=160$)

is adequate for at least 80% power. If either effect size is much smaller (simulations used 0.14), the study will be underpowered.

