9.4.2 ANALYSIS OF THE PRIMARY ENDPOINT(S)

The primary endpoints of MVPA, dietary risk, and veggie meter will be assessed using the linear model described in 9.4.1. A test of the appropriate interaction parameter at a significance level of 0.05 will serve as the test of the intervention's effect on each primary outcome.

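### The 9.4.1 model fits one baseline slope to weeks 16, 32 and 48: a small precision loss at week 48 if the baseline correlation fades, and bias only if baseline-dependent dropout also differs by arm

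*Combined protocol and SAP*

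**What the plan says.** Section 9.4.1 states that "a linear mixed model will be built for the outcome at all three follow-up timepoints (16, 32, and 48 weeks". Its fixed effects start with "intercept, value of the endpoint at baseline, timepoint (three parameters total, with baseline as the referent), intervention (control as the referent". A single interaction completes the list and lets the arm effect vary by visit: "intervention by timepoint interaction (three parameters total, allows for a different intervention effect at each timepoint". No baseline-by-timepoint term is listed.

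The same section includes a random intercept and says that "the within-subject covariance matrix will be chosen based in the lowest AIC among unstructured, compound symmetric, and first-order autoregressive". For the primary test it says: "The test of the outcome at 48 weeks will be a test of the coefficient for the intervention effect at 48 weeks".

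Section 9.4.2 applies this model unchanged to MVPA, dietary risk and veggie meter ("will be assessed using the linear model described in 9.4.1"), and 9.4.3 reuses it for the secondary and tertiary endpoints.

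Section 9.2 says that "The primary endpoint at 48 weeks post first group session is tested at a significance level of 0.05". Its power calculation assumes compound symmetry across all timepoints and says that "comparisons of complete data on 80 participants per group are assumed, and also assume 20% attrition". It gives correlations for BMI, WHR and A1C, and none for the three primary endpoints.

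**The concern.** With one baseline term, the model assumes that baseline predicts week 48 as strongly as week 16. If the relation weakens with time, the fitted slope is a compromise that sits above the true week-48 slope, so baseline is over-corrected at the visit on which the primary test rests. The AIC choice does not repair this: it concerns covariance among the follow-up residuals and leaves the baseline slope common, even when the unstructured form is chosen.

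Two things are at stake. One is precision at week 48, from a covariate that the trial already collects. The other is bias under incomplete follow-up. The model omits a week-48 term equal to (true slope minus common slope) times baseline. This cancels between arms when retained women have the same baseline distribution in each arm, and does not cancel when they differ.

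**Working it through.** **Inputs from the documents.** 200 women, 100 per arm; 80 per arm with complete data; 20% attrition, not split by arm or baseline (9.2). Week-48 alpha 0.05, taken as two-sided. Pilot attendance at the three follow-ups was 83%, 82% and 78% (2.2, Study 4).

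**The plan's own figures.** The enrolment figure reproduces: 160/(1 - 0.20) = 200. The nearest stated power is 85% for BMI (effect 0.56, correlation 0.35, 80 per group). Read as a change score, the SD is sqrt(2 x (1 - 0.35)) = 1.140, and power is Phi(0.56/1.140 x sqrt(80/2) - 1.96) = 0.87. That is close to 85% but not a match. The full software inputs are not shown and BMI is a secondary endpoint, so the loss below is expressed against a nominal 80%.

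**Assumed, because the documents give no values.** Unit-variance outcomes; the baseline-to-follow-up correlation patterns below; unstructured residual covariance.

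**Precision.** Let b16, b32, b48 be the true baseline slopes (equal to the correlations at unit variance) and R the residual covariance of the three visits given baseline. The common slope c minimises log det(R + (b - c)(b - c)'). Week-48 residual variance is 1 - b48^2 with visit-specific slopes and 1 - 2 c b48 + c^2 with a common slope. Their ratio is the variance inflation.

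- Worked case, pure AR(1) at 0.7 per 16 weeks: b48 = 0.343 and c = 0.593. Common: 1 - 2 x 0.593 x 0.343 + 0.593^2 = 0.945. Separate: 1 - 0.343^2 = 0.882. Ratio 1.071. Power: Phi(2.80/sqrt(1.071) - 1.96) = 0.77.
- Worked case, mild fading 0.6/0.5/0.4 with follow-up correlation 0.6: c = 0.526. Common: 1 - 2 x 0.526 x 0.4 + 0.526^2 = 0.856. Separate: 0.840. Ratio 1.019.

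| Assumed correlation with baseline | Variance ratio at week 48 | 80% power becomes |
|---|---|---|
| Constant (compound symmetry, as in 9.2) | 1.00 | 80% |
| Random intercept (share 0.4-0.6) plus AR(1) 0.3-0.6 | 1.006-1.036 | 78.6-79.8% |
| 0.6/0.5/0.4 | about 1.02 | about 79% |
| Pure AR(1), 0.5 to 0.9 | 1.044, 1.060, 1.071, 1.071, 1.050 | 77-78% |

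In the second row the correlation at lag k is w + (1 - w) x rho^k, where w is the intercept's share of variance. A steeper pattern still, 0.7/0.5/0.3, gives 1.08-1.16 depending on the follow-up correlation. It is a stress case.

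**Bias.** Data were simulated with no true effect and about 20% monotone dropout, logistic in baseline, and fitted by maximum likelihood with unstructured covariance. The patterns were pure AR(1) at 0.6-0.7 and random intercept plus AR(1). Week-48 bias in SD units:

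| Dropout depends on baseline | Common slope | Visit-specific slopes |
|---|---|---|
| Equally in both arms | about 0.00 | about 0.00 |
| In one arm only | about 0.02-0.05 | 0.01 or less |
| In opposite directions | about 0.05-0.10 | 0.01 or less |

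The lower ends belong to the random-intercept pattern and the upper ends to pure AR(1). With 200 women per trial, 1,000 simulated trials and pure AR(1) at 0.6-0.7, the opposite-direction case gave a false-positive rate of about 9%, against 5-6% with visit-specific slopes. The 0.7/0.5/0.3 pattern with about 24% dropout raises the biases to 0.073 SD (one arm) and 0.153 SD (opposite). Equal dropout still gives about zero.

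**The case against.** A single baseline main effect is a common and valid prespecification. Under randomisation it leaves the week-48 contrast unbiased with complete data, and also with baseline-dependent dropout that is the same in both arms. This stands. Three stronger readings may tempt a reader, and the documents do not support them.

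- **That the test is biased whenever dropout depends on baseline.** It is not: the misfit cancels when the dependence is the same in both arms. Section 9.2 gives one unsplit attrition figure, the pilot attendance shows no arm or baseline pattern, and 4.2 matches contact time between arms. Nothing points to differential dropout, although the arms differ in content and it cannot be excluded.
- **That offering AR(1) or unstructured covariance concedes that the correlation fades.** The candidate list also contains compound symmetry, and 9.2 assumes compound symmetry. A list of candidates is not evidence about the data.
- **That the common-slope adjustment is no better than no adjustment.** This appears only under pure AR(1) at 0.6 or below (0.5 and 0.6 give residual variance 1.03 and 1.01, against 1.00 unadjusted). Section 9.4.1 includes a random intercept, which puts a floor under the correlation. With that floor, the common slope still cuts variance by 17-46% against no adjustment.

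A further objection is one of order. With only three follow-up visits as responses and an intercept, two timepoint parameters can be estimated, not three with baseline as referent. The wording may mean that baseline is also a response row. If so, the baseline relation is carried by the covariance and this point falls away. That also stands, so the two edits belong together.

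**Conclusion.** The point holds as a minor one. Section 9.4.1 imposes one baseline slope on three visits, and no other section frees it. Under the plan's own compound symmetry nothing is lost. If the correlation fades, the likely cost at week 48 is about 1-4% of variance, with about 7% at the pure AR(1) end. Bias needs two conditions together, fading and a dropout-baseline relation that differs by arm; it is then about 0.02-0.05 SD for one arm, and 0.05-0.10 SD in the opposite-direction stress case. Every size rests on assumed correlations and an assumed dropout model. The case for acting is that the change costs almost nothing, not that the planned test is known to be invalid.

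**What to change.** In 9.4.1, add the fixed effect baseline value by timepoint, with timepoint coded over the three follow-up visits, so that each visit has its own baseline slope. Read the week-48 arm effect from that model for every primary, secondary and tertiary endpoint analysed under 9.4.1. Baseline does not interact with arm, so this contrast does not depend on how baseline is centred.

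In the same edit, state whether baseline is a covariate or a response row, and correct the parameter counts that take baseline as the referent. The new term applies only if baseline is a covariate and not also a response.

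The cost is one line of text and two extra parameters per model, with no new data and negligible loss if the correlation is in fact constant. The change should be made before unblinding, so that it cannot look data-driven.

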9.4.3 ANALYSIS OF THE SECONDARY ENDPOINT(S)

The secondary endpoints (BMI, % Body Fat, WHR, BP, and cytokines), dietary risk, and veggie meter will be assessed using the linear model described in 9.4.1. A test of the appropriate interaction parameter at a significance level of 0.05 will serve as the test the intervention's effect on each primary outcome.

The tertiary endpoints (mindfulness, stress management, positive reappraisal, self-regulation, and self-efficacy dietary risk, and veggie meter will be assessed using the linear model described in 9.4.1. A test of the appropriate interaction parameter at a significance level of 0.05 will serve as the test the intervention's effect on each primary outcome

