9.4.8 EXPLORATORY ANALYSES

Other timepoints: The intervention effect will be examined on the 16- and 32-week primary and secondary outcomes. Using the models described in 9.4.1, the intervention effect will be estimated at 16-

and 32-weeks using the appropriate interaction parameters. These tests will be conducted at an alpha level of 0.025; this alpha level was selected using a Bonferroni correction because each outcome has two tests.

Mediation: mediation of the intervention effect on the primary outcomes will be tested by each of the tertiary outcomes over 48 weeks. To account for temporal precedence, these analyses will use values for mediators measured at 32 weeks and primary outcome measured at the end of 48 weeks. Mediation will first be assessed using each of the three potential mediators one at a time and then in combination, to assess the possibility of multiple mediation.

The indirect effect of the intervention will be estimated via the mediator(s), along with a 95% bias-corrected bootstrapped confidence interval. This effect will be interpreted to the extent that it is in a direction consistent with the mediation hypothesis. It is important to estimate and test for mediation even if there is no evidence of an overall intervention effect. It is possible that the test of mediated effect has more statistical power, and mediation can be found in the absence of an overall effect.

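### The model in 9.4.1 uses follow-up visits only but codes time against baseline, so the single interaction parameter named as the primary test in 9.4.2 is not uniquely defined.

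*Combined protocol and SAP*

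**What the plan says.** Section 9.4.1 says twice which visits supply outcome rows: "a linear mixed model will be built for the outcome at all three follow-up timepoints (16, 32, and 48 weeks" and, in the paragraph on covariance, "For the primary outcome, modeled at the three follow-up visits". The baseline value enters as a covariate.

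The same section lists the fixed effects: an intercept, the baseline value, "timepoint (three parameters total, with baseline as the referent", an intervention effect with control as referent, and three intervention-by-time interactions, one per follow-up visit. It then states the target: "The test of the outcome at 48 weeks will be a test of the coefficient for the intervention effect at 48 weeks".

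Section 9.4.2 names the test for MVPA, dietary risk and veggie meter: "A test of the appropriate interaction parameter at a significance level of 0.05 will serve as the test". Section 9.4.3 uses the same device for the secondary and tertiary endpoints. Section 9.4.8 uses it for the earlier visits, where effects are to be estimated at 16 and "32-weeks using the appropriate interaction parameters".

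The power calculation in 9.2 pairs the between-group contrast with "the appropriate within-group contrast (three post-baseline timepoints versus baseline".

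**The concern.** A factor cannot take as referent a level that has no rows. If baseline is only a covariate, the time factor has three levels. Three time columns plus an intercept are then one column too many, and three interactions plus an arm main effect are again one too many. The listed parameters suit a data set in which baseline is stacked as a fourth outcome row, which 9.4.1 rules out.

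What is at stake is the named primary test. If a single interaction parameter has no unique value, two analysts who follow 9.4.2 to the letter with different software defaults can report different numbers from the same data. Which contrast is primary should not be settled after the data are in hand.

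**Working it through.** **Inputs.** Three outcome rows per participant and the list of fixed effects, both from 9.4.1; 80 analysed participants per arm, from 9.2. The sample size only sets the dimensions and does not affect the rank.

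**Column count.** Intercept 1 + baseline value 1 + time 3 + arm 1 + interaction 3 = 9. Rows: 160 × 3 = 480.

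**Rank.** Every row belongs to exactly one of the three follow-up weeks, so on every row:

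- intercept = t16 + t32 + t48
- arm = arm×t16 + arm×t32 + arm×t48

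That makes two exact dependencies, and 9 − 2 = 7. Building the 480 × 9 matrix numerically also gives rank 7. Both dependencies hold row by row, so missing visits do not remove them. The random intercept and the choice of covariance structure do not alter the fixed-effects columns.

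**Estimability.** A contrast is estimable only if it is orthogonal to both dependency vectors. With the coefficients ordered (intercept, baseline, t16, t32, t48, arm, int16, int32, int48), these are (1, 0, −1, −1, −1, 0, 0, 0, 0) and (0, 0, 0, 0, 0, 1, −1, −1, −1).

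| Contrast | Product with second vector | Estimable |
|---|---|---|
| arm alone | 1 | no |
| int48 alone (likewise int16, int32) | −1 | no |
| arm + int48 | 1 − 1 = 0 | yes |
| int48 − int16 | −1 + 1 = 0 | yes |

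All four contrasts have product 0 with the first vector.

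**Illustration.** One simulated data set (80 per arm, true effects 0.2, 0.3 and 0.5 at weeks 16, 32 and 48) was fitted by ordinary least squares under four ways of resolving the aliasing. The residual sum of squares was 553.945 each time.

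| Resolution | arm | int48 | arm + int48 |
|---|---|---|---|
| week-48 columns set to zero | 0.5521 | 0.0000 | 0.5521 |
| week-16 columns set to zero | 0.0605 | 0.4915 | 0.5521 |
| intercept and arm set to zero | 0.0000 | 0.5521 | 0.5521 |
| Moore-Penrose inverse | 0.2179 | 0.3342 | 0.5521 |

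In the second line int48 is the week-48 effect minus the week-16 effect (0.5521 − 0.0605 = 0.4916, equal to 0.4915 up to rounding). The rows of int48 values are therefore different quantities, and only the sum is stable.

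**Codings that work.** Follow-up rows with the baseline value, three week terms and three arm-by-week terms, without intercept or arm main effect: 7 columns, rank 7, and int48 is itself the 48-week effect. The nine listed columns become full rank (640 × 9, rank 9) if baseline rows are stacked as outcomes. Baseline is then both outcome and covariate, and the two follow-up-only statements are contradicted.

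**Link to 9.2.** With n per arm, common variance σ² and compound symmetry with correlation ρ:

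- difference in change from baseline: variance (2σ²/n) × 2(1 − ρ)
- baseline-adjusted difference: variance (2σ²/n) × (1 − ρ²)
- ratio: 2(1 − ρ) / [(1 − ρ)(1 + ρ)] = 2/(1 + ρ)

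For ρ from 0 to 1 the ratio falls from 2 to 1; at an assumed ρ of 0.5 it is 2/1.5 = 1.33. Under randomisation both contrasts have the same expectation.

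**The case against.** The best reply is that a competent statistician would know what is meant. Section 9.4.1 gives the rows twice, lists baseline as a covariate, describes interactions that let the effect differ by visit, and names the 48-week intervention effect as the target. That effect is unique. Once the redundant intercept and arm columns are dropped, the week-48 interaction is the 48-week effect, so 9.4.1 and 9.4.2 can be reconciled by recoding alone. This stands, and it limits the point to parameterisation and naming. It does not remove it: in the coding as listed no single coefficient equals the 48-week effect, and the plan gives no constraint or contrast that would make one do so.

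Three stronger readings are tempting, and the documents do not support them.

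- *The primary analysis cannot be run.* The 48-week effect is estimable from the listed model as arm plus arm-by-week-48.
- *The primary test is an interaction against a follow-up referent, blind to a sustained effect.* Software may return that quantity, but the text does not intend it. Section 9.4.1 has three interaction parameters, whereas a follow-up referent leaves two, and 9.4.8 expects an effect at week 16 as well.
- *A stated amount of power is lost.* The loss would be measured against the stacked layout that 9.4.1 excludes. The documents give no correlation or effect size for the primary endpoints. Checking against the powers stated in 9.2 for BMI and waist-hip ratio depends on the significance level (0.05 or 0.025) and on an effect-size scale that is not given.

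Nor do the change hypotheses in 9.1 conflict with baseline adjustment: with the baseline value in the model, analysing change or follow-up value gives the same arm effect.

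**Conclusion.** The plan is wrong as written and should be fixed before analysis. On the rows that 9.4.1 specifies, nine columns have rank 7, and the single interaction parameter that 9.4.2 makes the primary test has no unique value. The same holds for the tests in 9.4.3 and 9.4.8. The rank result is algebra and needs no assumption about the data; the simulated values only illustrate it.

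The model space and the 48-week effect are intact, and no bias is alleged. The mismatch with 9.2 is secondary. Its power contrast is the between-group difference in change from baseline, while the analysis contrast in 9.4.1 is baseline-adjusted. The two agree in expectation and differ in variance by 2/(1 + ρ), assuming compound symmetry and equal variances. No power figure is claimed.

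**What to change.** - **9.4.1:** delete the clause that makes baseline the time referent. State that the outcome rows are weeks 16, 32 and 48 only, and that the fixed effects are the baseline value, three week terms and three arm-by-week terms, with no separate intercept or arm main effect (or an equivalent full-rank coding). Define the primary test as the baseline-adjusted arm difference at week 48.
- **9.4.2, 9.4.3 and 9.4.8:** replace the references to an appropriate interaction parameter with the matching visit-specific arm difference (week 48, or weeks 16 and 32 in 9.4.8).
- **9.2:** add one sentence saying that the power contrast, the between-group difference in change from baseline, is not the baseline-adjusted contrast used in the analysis.

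The cost is wording in four sections and one sentence in a fifth. No new data or assessments are needed. The change should be dated before outcome data are analysed by arm.

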Study 4: 68 AA adults were enrolled to compare a mindfulness-based pre-diabetes (MPD) prevention program to a conventional diabetes prevention program for AA adults (>80% AAW) with pre-diabetes (Grant # R21 AT004276-03),^{76,51} using a mixed-methods, two-arm RCT. Participants reported acceptability, credibility, and cultural-relevance of the intervention. Enrollment of eligible participants (79%), session attendance (76.5%), retention (90%), and attendance at three post-intervention data collection sessions (83%, 82%, and 78%, respectively) demonstrated feasibility. MPD resulted in reductions in perceived stress and BMI, reduced calorie, fat, and carbohydrate intake, and improved quality of life. Both groups reported increased knowledge about strategies to improve diet and exercise. MDP participants reported using mindfulness, breathing techniques, and conscious eating behaviors, and were more aware of stress. Participants recommended improvements that form the basis for this proposal: 1) explicit discussion of the potential impact of culturally-relevant, contextualized stressors for AAW; 2) incorporation of strategies in the mindfulness sessions for overcoming guilt and resistance to self-sacrifice by enhancing self-compassion; and 3) incorporating strategies to help AAW overcome physical and psychological barriers to home-based mindfulness practice, exercise, and healthy eating (e.g., accountability partners).

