4 STUDY DESIGN

4.1 OVERALL DESIGN

The HARMONY study is a two-arm, randomized control, single site trial to test the HARMONY experimental group against an attention control group (Nutrition and Exercise Education Workgroup; NEEW). The study will be conducted in 8 cohorts of 25 participants, group sizes of 12-13 randomly assigned to HARMONY and 12-13 to NEEW. The allocation sequence will be generated using permuted blocks (2,4,6). Participants will be told after baseline assessment to anticipate a brief wait (~4 weeks) until 25 participants are accrued in the cohort, at which time participants will be randomized.⁷⁷

The main study hypothesis is that the HARMONY intervention will promote and sustain improvements in health behaviors that lower CM risk factors in AAW through improved management of stress.

HARMONY is an intervention to help AAW manage chronic stress and develop and sustainable new healthy habits for exercise and eating as a means of self-care, despite pervasive environmental and sociocultural challenges and caregiving demands. A 16-week program using an approach based on mindfulness, HARMONY is designed to be scaled and translated for use in community settings serving AAW. Unique in length and focus on managing culturally-relevant stressors specific to AAW, who face high CM risk, HARMONY – unlike nutrition and exercise-only active control interventions – focuses specifically on mindful self-management of negative emotions and behaviors that may impact adherence to sufficient self-care engagement, adequate exercise, and/or healthy eating habits.^{50,78, 79} The goal of HARMONY is to provide AAW with strategies to address stress cognitively and emotionally in a way that simultaneously honors their desire to care for their families and communities while harmoniously and successfully integrating sustained engagement in exercise and healthy eating through improvements in mindfulness, positive reappraisal, self-regulation, and self-efficacy. Accordingly, AAW will have reduced psychological distress and improved resilience to stress,⁸⁰⁻⁸² address barriers to sustaining their healthy lifestyle changes.

The NEEW group includes only the culturally tailored nutrition education and exercise program, which does not address mindfulness, positive reappraisal, self-regulation, and self-efficacy, stress management, or SWS.

Participants will be engaged for approximately 13 months, which includes the following:

- Screening telephone call

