- Pre-baseline period
- Baseline visit
- 8 biweekly HARMONY/NEEW sessions over a 16-week period (e.g., weeks 1, 3, 5, 7, 9, 11, 13, 15),
- 6 monthly booster sessions.
- Follow-up assessments at 16, 32, and 48 weeks post first group session

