6.1.2 ADMINISTRATION

The HARMONY and NEEW interventions will be delivered over 8 every-other-week sessions and 6 booster sessions. All intervention sessions will be led by various interventionists:

- A personal trainer to facilitate the exercise portion of the session;
- A health educator (not trained in mindfulness) who will deliver the CM prevention and risk-reduction education; and
- A mindfulness instructor who will deliver the mindfulness cool down (for HARMONY group only).

The personal trainer and health educator will lead both the HARMONY and NEEW groups, however they will be instructed to not speak about the other group to ensure blinding.

Participants will interact with others in their group during the study but will not have contact with participants outside of their group. A “buddy system” will also be implemented where participants will be encouraged to communicate with their buddy to enhance accountability.

All intervention sessions will be delivered over secure teleconferencing platforms (e.g. Zoom) due to the COVID-19 pandemic.

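### The 9.4.1 model and the 9.2 power calculation ignore the 8 cohorts and 16 closed delivery groups, so the week-48 tests may be too liberal or slightly conservative, and the plan gives no way to tell which

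*Combined protocol and SAP*

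**What the plan says.** **Design.** Section 4.1: "The study will be conducted in 8 cohorts of 25 participants, group sizes of 12-13 randomly assigned to HARMONY and 12-13 to NEEW". Each cohort is filled to 25 before it is randomised, so both arms are drawn from the same cohort and there are 8 x 2 = 16 delivery groups, each wholly in one arm.

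**Delivery.** Section 6.1.2: "Participants will interact with others in their group during the study but will not have contact with participants outside of their group". A buddy arrangement "will also be implemented where participants will be encouraged to communicate with their buddy to enhance accountability". The mindfulness instructor works in HARMONY only, but "The personal trainer and health educator will lead both the HARMONY and NEEW groups". All sessions are by teleconference. Section 4.1 lists 8 biweekly sessions and "6 monthly booster sessions". Section 4.2 supports the group size partly by the cohesion such groups have produced before, and 8.1 measures group cohesion at sessions 2 and 7.

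**Analysis.** The 9.4.1 model has fixed effects for baseline value, timepoint, intervention and their interaction, a within-subject covariance chosen by AIC, and one random effect: "A random intercept will be included to account for within-participant correlation". Sections 9.4.2 and 9.4.3 reuse it for the primary, secondary and tertiary endpoints.

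**Power.** Section 9.2 takes 80 completers per arm after 20% attrition and compound symmetry across timepoints. It states 85% power for BMI at an effect size of 0.56. No cohort or group correlation or design effect appears.

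**The concern.** Women who spend months in the same closed group may come to resemble each other in exercise and diet. Each group lies in one arm, so any such resemblance goes straight into the arm contrast. A model with only a participant intercept does not see it, and its standard error is then too small.

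The cohort works the other way. Season, recruitment wave and shared staff affect both arms of a cohort alike and cancel in the contrast. A model without a cohort term leaves that variance in the error, and its standard error is then too large.

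At stake are the size of the three week-48 primary tests at 0.05 and the meaning of the stated power. The 16- and 32-week tests at 0.025 are affected in the same way, but 9.4.8 places them among the exploratory analyses.

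**Working it through.** **The plan's own figures.** 160/(1 - 0.20) = 200 reproduces, so the sample size allows for attrition and nothing else. For BMI, correlation 0.35 gives a change SD of sqrt(2 x 0.65) = 1.140. The noncentrality is 0.56/(1.140 x sqrt(2/80)) = 3.106, and power is 0.874 at two-sided 0.05 or 0.806 at 0.025. The stated 85% is close to the first but not reproduced exactly. That is a separate matter; 85% is taken at face value below.

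**Inputs.** k = 8 cohorts (4.1) and 80 completers per arm (9.2), so m = 80/8 = 10 completers per group. The pilot's last-visit attendance of 78% (2.2) gives 12.5 x 0.78 = 9.75, much the same. The week-48 alpha is 0.05, taken as two-sided. **Assumed, because no document gives them:** g = delivery-group ICC beyond cohort; c = cohort ICC shared by both arms.

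**Variance.** Set the total variance to 1, made up of c (cohort), g (group) and 1 - g - c (person). The difference between arm means, averaged over 8 cohorts, has variance

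(2/8) x [g + (1 - g - c)/m] = (2/(8m)) x [1 + (m - 1)g - c].

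The planned model assumes about 2/(8m). At m = 10 the ratio is r = 1 + 9g - c.

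**Actual alpha at nominal 0.05**, 2 x [1 - Phi(1.960/sqrt(r))]. In brackets is the rejection rate of a test with no cohort or group term, from 40,000 simulated null trials of 8 cohorts x 2 arms x 10:

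| g | c = 0 | c = 0.05 | c = 0.10 |
|---|---|---|---|
| 0 | 0.050 (4.9%) | 0.044 (4.5%) | 0.039 (4.0%) |
| 0.01 | 0.060 (5.9%) | 0.055 (5.5%) | 0.049 (4.9%) |
| 0.02 | 0.071 (7.1%) | 0.065 (6.8%) | 0.059 (6.1%) |
| 0.05 | 0.104 (10.5%) | 0.098 (10.1%) | 0.092 (9.4%) |

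A within-cohort comparison of arm means on 7 df rejected 4.8-5.2% throughout.

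**The break-even is approximate.** With only 8 cohorts, expected variances balance nearer c = 10.3g than 9g. At exactly 9:1 the simulated error was 5.2% at g = 0.01 and 6.3% at g = 0.05. With no dropout the multiplier is 12.5 - 1 = 11.5, not 9.

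**A cohort effect alone does not repair the test.** With cohort fitted as a fixed effect and no group term, simulated rejection at c = 0.05 was 7.6% at g = 0.02 and 11.0% at g = 0.05.

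**Power of a correctly sized 7-df test.** The stated 85% at alpha 0.05 implies a noncentrality of 1.960 + 1.036 = 2.996. Divide by sqrt(r) and use the noncentral t with critical value 2.365:

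| g | c = 0 | c = 0.05 | c = 0.10 |
|---|---|---|---|
| 0 | 73% | 75% | 77% |
| 0.01 | 69% | 71% | 73% |
| 0.02 | 66% | 68% | 70% |
| 0.05 | 57% | 59% | 60% |

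If the 85% refers to alpha 0.025, the g = 0, c = 0 cell becomes 80%.

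**The case against.** The strongest reply is that the size of the problem is wholly assumed. The trainer and health educator serve both arms, delivery is by teleconference, and if the boosters follow the 16-week programme directly, sessions end around week 40-42, before the week-48 assessment. The HARMONY-only instructor adds between-group variance only if instructors differ between cohorts, which 6.1.2 does not say. At g = 0.005 and c = 0.05 the formula gives alpha 0.049, which is no inflation. All of this stands, and it is why no direction can be asserted. It does not show that g is near zero: peer contact and buddies remain, and 8.1 still asks about buddy contact at 48 weeks.

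A second reply is that a strict 7-df test costs real power to cure what may be a small error: at g = 0.01, c = 0.05 it trades alpha of 0.055 for power of about 71%. That cost is real. It argues for declaring the choice now, and for a mixed model that keeps all visits as the main analysis rather than a comparison of week-48 means that discards participants.

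A reader might go further and infer that the primary tests run at 10% or more, or that the trial is underpowered. The documents support neither. Alpha near 0.10 needs g of about 0.05, and no section gives an ICC for accelerometer activity, dietary risk or skin carotenoids. The only power figures are for secondary endpoints, so none exists for a primary endpoint to be reduced.

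**Conclusion.** The omission is certain: 9.2 and 9.4.1-9.4.3 contain nothing for cohort or delivery group and no argument that they can be ignored. Its effect is conditional. The week-48 tests are anti-conservative when 9g clearly exceeds c and mildly conservative when c dominates, with an approximate boundary that rests on about 10 completers per group. Over assumed g of 0.01-0.05 and c of 0-0.10, actual alpha is about 0.05 to 0.10. The value for MVPA, dietary risk or veggie meter is unknown. This should be fixed because it bears on the error term of the primary tests, but it is not evidence that those tests are badly inflated.

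**What to change.** **Section 9.4.1.** Add cohort and a delivery-group random effect (cohort x arm, 16 levels) to every primary, secondary and tertiary model that uses this section. Keep all three follow-up visits and all participants. Name a small-sample degrees-of-freedom method that reflects 8 cohorts. State that the group term stays in whatever its estimate: for g up to 0.02, the simulated estimate was at or below zero in 42-57% of trials, so a rule that drops it on that basis would do so about half the time.

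**Fallback or sensitivity analysis.** Pre-specify a within-cohort comparison of baseline-adjusted arm means (7 df). Note that a version using week-48 data alone loses women without that visit.

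**Section 9.2.** Say that the quoted power assumes no clustering. Restate power, including for the three primary endpoints, over a stated range of g and c that includes g = 0.

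**Cost.** A protocol amendment with IRB approval, and a delivery-group variable in the analysis dataset (6.4 already documents session attendance). No extra participants or visits. Intervals widen: on 7 df the critical value is 2.365 against 1.960, about 21% at g = c = 0. Taking the BMI 85% at face value, power becomes about 73-77% with no group effect and 66-70% at g = 0.02, for c of 0-0.10.
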